7.2 Study Conduct

Relevant protocol deviations, which could have a major impact on the interpretation of the study results, will be identified prior to the unblinding of the database for all subjects who are randomized and receive double-blind medication.

Relevant protocol deviation criteria, including an assessment of the impact of any Covid-19 related deviations observed are listed in [APPENDIX 1](#).

All subjects with relevant protocol deviations will be identified prior to the final database lock and unblinding of treatment assignment. All relevant protocol deviations will be listed and summarized by treatment group.

Following a case by case review of all incidences of Covid-19 related events (scheduling of visits, accurate receipt of medication) the impact of Covid-19 on the primary endpoint is considered minimal. The Per-Protocol analysis will exclude subjects with Covid-19 related deviations that could potentially impact the primary endpoint.

7.3 Study Population

Summary statistics of data pertaining to subject disposition, demographics, baseline characteristics, and medical history, including form of IIM, will be tabulated and displayed by randomized treatment group. No statistical test will be carried out for comparison of any baseline measurement between treatment groups.

These presentations will use the ITT analysis population and will be for “as-randomized” treatment regimen.

7.3.1 Subject Disposition

The disposition of subjects in the double-blind period will be presented as follows:

- Number of subjects enrolled at screening.
- Number of subjects randomized.
- Number of subjects treated in the double-blind period (i.e. who received at least 1 dose of study drug (abatacept or placebo).
- Number of subjects who discontinued during the double-blind period, together with reasons for discontinuation (taken from the eCRF status page).
- Number of subjects who completed the double-blind period, but who did not enter the open-label period and reason for not entering the open-label period (taken from the eCRF status page).

7.3.2 Demography and Baseline Disease Characteristics

Demographic and baseline disease characteristics will be summarized using the ITT analysis population. The summaries will be presented by as randomized treatment group and overall.

Continuous variables will be summarized using means and standard deviations, and categorical variables will be summarized using frequency distributions. The characteristics will be summarized based on the data captured on the CRF page, except for the randomization stratification which will be based on the IXRS data.

The following demographic and baseline characteristics will be summarized:

- Age.
- Age group (16-29, 30-39, 40-49, 50-59, \geq 60 years).
- Gender.
- Race.
- Ethnicity.
- Geographic region:
 - North America: Canada and United States
 - South America: Argentina, Brazil, Chile, Columbia and Peru.
 - Europe: Italy, Romania, Russia, Spain and Turkey.
 - Asia: China, Hong Kong, Japan, Korea, and Taiwan.
 - Rest of World (ROW): Australia, Israel.
- Weight.
- Weight group (< 60, 60-100, > 100kg).
- Stratification factor Region (Japan vs. ROW).
- Stratification factor Disease diagnosis (DM vs. Non-DM).
- Stratification factor ILD (absent vs. present).
- Disease diagnosis: IIM type (DM, PM, autoimmune necrotizing myopathy).
- Randomization strata, Japan/Other, Disease Diagnosis; ILD:
 - Japan/Non-DM with ILD present.
 - Japan/Non-DM with ILD absent.
 - Japan/DM with ILD present.
 - Japan/ DM with ILD absent.
 - Non-Japan/Non-DM with ILD present.
 - Non-Japan/Non-DM with ILD absent.
 - Non-Japan/DM with ILD present.
 - Non-Japan/DM with ILD absent.
- Duration of disease in months.
- Duration of disease by disease diagnosis (DM vs. Non-DM).
- Medication History:
 - Number of prior medications used to treat Myositis: corticosteroids, immunosuppressant's, or biologics (1, 2, 3, > 3).
 - Number of prior DMARDS.

- Number of current background Myositis medications: corticosteroids, immunosuppressant's (1, 2, 3, > 3).
- CK level at screening (continuous variable): number of subjects with elevated CK > 5 times the upper limit of normal at screening.
- Muscle enzyme levels (CK, AST, ALT, LDH, aldolase) at baseline (continuous variable).
- Baseline Physician's global assessment.
- Baseline Subject's global assessment.
- Baseline MMT-8.
- Baseline HAQ-DI (continuous variable).
- Baseline Myositis Function Index (FI-2) scores (continuous variables).
- Baseline Extramuscular Global Activity (as assessed by MDAAT).
- Baseline CDASI scores (continuous variables)
- Baseline MDI scores (continuous variables).

Any imbalances between treatment groups for the characteristics described above will be assessed when reviewing the summary tabulations and any differences deemed clinically relevant to the primary efficacy comparisons may be investigated by controlling for the characteristic in a supplemental analysis.

7.3.3 Medical History and Prior Medication

General medical history will be provided in a listing for the ITT analysis population.

Prior medications are defined as medications a subject started to take prior to the first SC injection of double-blind study medication. Prior medications will be summarized for each treatment group by drug class, generic name for the ITT analysis population.

Medications of special interest to Myositis treatment are the following categories: steroid and other steroid-sparing medications based on the WHO dictionary. A summary of prior medications of special interest will be provided by treatment group.

7.4 Extent of Exposure

7.4.1 Study Therapy

Because dosing for the open-label period, the open-label extension period (Japan) and the long-term extension period is collected on the same CRF, visit dates recorded on CRF pages that correspond to the first/last visits within these periods will be used to distinguish these periods and the exposure periods will be defined by visit start and end dates of visit periods recorded on the CRF.

7.4.1.1 Exposure during Double-Blind Period

Extent of exposure to double-blind study drug will be summarized using the as-treated analysis population in two ways:

- Number of injections.
- Number of days a subject is known to be on study drug.

The number of injections subjects received will be based on the study medication page of the CRF when an injection date is present.

The number of days the subject is known to be on study drug (exposure to study drug) during 24-week double-blind period is calculated as:

- For subjects who discontinued during 24-week double-blind period or did not enter the open-label period within 56 days of the last injection in the double-blind period:
- Exposure in days = (date of last injection in the 24-week double-blind period - date of first injection for double-blind period + 1) + 56.

For subjects who enter open-label period within 56 days of the last injection of 24-week double-blind period:

- Exposure in days = (date of first injection in the open-label period - date of first injection in the double-blind period).

The offset of 56 days is the length of 2 regular dosing cycles and represents approximately 4 times the half-life of abatacept in humans.

Summaries of exposure to study drug will show the distribution of the number of injections and days on drug, together with the means, standard deviations, medians, minima and maxima, by treatment group.

7.4.1.2 Exposure during Open-Label Period

The exposure to study drug during the open-label period will be calculated as follows:

Exposure to study drug in days for subjects who discontinued open-label period prior to the analysis cutoff date for the 24-week analysis is calculated as:

- Exposure in days = (date of last dose of study drug in the open-label period - date of first dose of study drug in open-label period + 1) + 56.

For subjects who are continuing beyond the analysis cutoff date for the 24-week analysis exposure is calculated as:

- Exposure in days = (data cutoff date - date of first dose of open-label period + 1).

The data cutoff date is the date of the last data change in the database prior to the DB lock.

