6 STUDY PERIODS, TREATMENT REGIMENS AND POPULATIONS FOR ANALYSES

6.1 Study Periods

There are 6 analysis periods defined for the study: the 5 study periods ((i) pre-treatment period; (ii) 24-week DB period; (iii) the OL period; (iv) the OLE period for Japan; (v) the LTE period, incorporating the OLE period for Japan) and (vi) the cumulative abatacept period. These periods will be used in the safety summaries.

The pre-treatment period: covers the time period prior to the first dose date/time of study medication.

The 24-week Double-Blind period: starts at the first dose date/time of double-blind study medication and lasts until the last dose date of the double-blind period + 56 days if subjects discontinue the study during double-blind period, or until the first dose in the open-label period.

Since the dosing information for the Open-Label period, the Open-Label Extension period and the Long-Term Extension period is recorded on the same CRF page, it is not possible to derive the first/last dose for the different periods based on that CRF page. This is why start and end visit dates from other CRF pages will be used to distinguish between these 3 periods. Start and end visit dates are recorded for most periods, except the start of the OLE period for Japan subjects, this will be

assumed to be the end of the OL period. These dates will be used for deciding which dose belongs to which period.

The Open-Label period: starts at the first dose of the open-label period and lasts until the last dose date of open-label period + 56 if subjects discontinue the study during open-label period (or if subjects are from U.S. and Czech Republic sites), or until the first dose in the open-label extension period for subjects from Japanese sites, or the first dose in the long-term extension period for subjects from other sites.

The Open-Label Extension period (Japan subjects only): starts at the first dose of the open-label extension period (determined as the open-label period end visit date from the CRF) and lasts until the last dose date of open-label extension period + 56 if subjects discontinue the study during open-label extension period, or until the first dose in the long-term extension period.

The Long-Term Extension period (all subjects except for U.S. or Czech subjects): starts at the first dose of the long-term extension period and last until the last dose date of long-term extension period + 56.

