7.4.1.3 Exposure during Open-Label Extension Period

The exposure to study drug during the open-label extension period will be calculated as follows:

Exposure to study drug in days for subjects who discontinued open-label extension period prior to the analysis cutoff date for the 28-week analysis is calculated as:

- Exposure in days = (date of last dose of study drug in the open-label extension period - date of first dose of study drug in open-label extension period + 1) + 56.

For subjects who are continuing beyond the analysis cutoff date for the 28-week analysis exposure is calculated as:

- Exposure in days = (data cutoff date - date of first dose of open-label extension period + 1).

The start date of the OLE period is not recorded for Japan subjects but is assumed to be the end date of the OL period.

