7.4.1.4 Exposure during Long-Term Extension Period

The exposure to study drug during the long-term extension period will be calculated as follows:

Exposure to study drug in days for subjects who discontinued long-term extension period prior to the analysis cutoff date for the 24-week analysis is calculated as:

- Exposure in days = (date of last dose of study drug in the long-term extension period - date of first dose of study drug in long-term extension period + 1) + 56.

For subjects who are continuing beyond the analysis cutoff date for the 24-week analysis exposure is calculated as:

- Exposure in days = (data cutoff date - date of first dose of long-term extension period + 1).

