11.5.1.1 Open-Label Period Exposure

The extent of exposure for the open-label period will be calculated and presented in days as follows:

- For subjects who discontinued during the open-label period or did not enter the open-label extension period or the long-term extension period within 56 days of the last injection in the open-label period:
- Exposure in days = (date of last injection in the open-label period - date of first open-label injection + 1) + 56.

For subjects who enter open-label extension or long-term extension period within 56 days of the last injection in the open-label period:

- Exposure in days = (date of first injection in the open-label extension or long-term extension period - date of first open-label injection).

The offset of 56 days is the length of 2 regular dosing cycles and represents approximately 4 times the half-life of Abatacept in humans.

Summaries of exposure to study drug will show the distribution of the number of injections and days on drug, together with the means, standard deviations, medians, minima and maxima, by treatment group.

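### SAP 7.4.1.2 gives no workable Week 24 open-label exposure rule for subjects who had completed the open-label period before the cutoff

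*SAP*

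**What the plan says.** SAP Section 1 states that the main text covers the Week 24 analysis and that Appendix 3 covers the three later ones. Section 7.4.1.2 therefore governs open-label exposure in the Week 24 report. It has two cases.

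- Discontinued: "Exposure to study drug in days for subjects who discontinued open-label period prior to the analysis cutoff date for the 24-week analysis is calculated as" last dose minus first dose plus 1, plus 56 days.
- Continuing: "For subjects who are continuing beyond the analysis cutoff date for the 24-week analysis exposure is calculated as" follows, and the formula is "Exposure in days = (data cutoff date - date of first dose of open-label period + 1"). The cutoff is one date for the whole database: "The data cutoff date is the date of the last data change in the database prior to the DB lock".

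The extension sections use the same template. For the Japan open-label extension, 7.4.1.3 has "Exposure in days = (data cutoff date - date of first dose of open-label extension period + 1"). For the long-term extension, 7.4.1.4 has "Exposure in days = (data cutoff date - date of first dose of long-term extension period + 1").

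Elsewhere the SAP sets other limits on the open-label period.

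- Section 6.1 ends it at the first dose of the Japan extension, "or the first dose in the long-term extension period for subjects from other sites", or 56 days after the last open-label dose for subjects who discontinue and for U.S. and Czech sites.
- The lead-in to 7.4.1 says that exposure periods are bounded by visit start and end dates on the CRF.
- Section 11.5.1.1, for the later analyses, has for subjects who move on within 56 days: "Exposure in days = (date of first injection in the open-label extension or long-term extension period - date of first open-label injection"). Those who do not move on get last minus first injection plus 1, plus 56.

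**The concern.** Section 7.4.1.4 provides for subjects who had discontinued the long-term extension before the Week 24 cutoff, so the SAP expects some subjects to have finished the open-label period by then. For them, 7.4.1.2 offers either a formula that runs on through the extension or no formula at all. Section 7.4.2 narrows the first case further: a subject counts as discontinued from a period only if the status page shows that the period was not completed. A subject who completed the open-label period and then left is neither discontinued nor continuing.

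At stake is the exposure table that describes how long subjects received open-label abatacept up to the Week 24 lock. Two programmers could follow the text and produce different figures, and one set could exceed the planned 28 weeks by a wide margin.

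**Working it through.** **Inputs.** The open-label period is 28 weeks (SAP 2.1). The first open-label dose is on Day 169 and the period ends on Day 365 (Protocol Table 5.1-3). The last open-label dose is in Week 51 (Protocol 4.5.1), that is Day 51 × 7 + 1 = 358. The Japan extension ends on Day 533 (Protocol Table 5.1-5). No lock date is given, so the time from long-term extension entry to cutoff, x, is assumed. Subjects are taken to be on schedule.

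**The plan's own figure.** 28 × 7 = 196 days, and 365 − 169 = 196. The formula in 11.5.1.1 returns 196 for anyone who moves straight into an extension, whatever the cutoff.

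**Literal reading of 7.4.1.2, outside Japan.** Open-label exposure = 196 + x + 1. Long-term extension exposure under 7.4.1.4 = x + 1. Days elapsed from first open-label dose to cutoff, inclusive = 196 + x + 1.

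| x (assumed) | Open-label, 7.4.1.2 | Long-term, 7.4.1.4 | Sum | Elapsed | Open-label ÷ 196 |
|---|---|---|---|---|---|
| 28 | 225 | 29 | 254 | 225 | 1.15 |
| 90 | 287 | 91 | 378 | 287 | 1.46 |
| 182 | 379 | 183 | 562 | 379 | 1.93 |
| 365 | 562 | 366 | 928 | 562 | 2.87 |

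In every row the sum exceeds elapsed time by exactly the long-term extension figure, so all of that time is counted twice.

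**Literal reading, Japan, x = 182.** The cutoff is Day 533 + 182 = 715.

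- Open-label: 715 − 169 + 1 = 547.
- Japan extension: 715 − 365 + 1 = 351.
- Long-term extension: 715 − 533 + 1 = 183.
- Sum: 547 + 351 + 183 = 1,081, against 547 elapsed.

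**Narrow reading.** If the second case means subjects still in the open-label period at the cutoff, the double count disappears. Subjects in an extension at the cutoff then fit neither case. Nor do subjects who completed the open-label period and stopped during an extension before the cutoff.

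**Completers who entered no extension.** They have no value in 7.4.1.2 on either reading. Under 11.5.1.1 an on-schedule completer gets (358 − 169 + 1) + 56 = 246 days.

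**The case against.** The strongest reply is that the text is terse rather than wrong. The section is headed as open-label exposure and its first case concerns discontinuing that period, so the second case naturally means continuing in it. The lead-in to 7.4.1 also bounds each period by CRF visit dates, which could act as a cap. These are fair readings, and for that reason double counting cannot be called certain. But the explicit formula uses a database-level cutoff and no period end date, so the lead-in conflicts with it instead of completing it. The narrow reading leaves subjects already in an extension without a rule. Section 7.4.1.1 shows that the authors knew how to write the hand-off: it ends double-blind exposure at the first open-label injection.

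Three further objections stand.

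- A reader might infer that U.S. and Czech completers are overlooked throughout the SAP. They are not: 6.1 ends their open-label period 56 days after the last dose. That defines a period for safety summaries, however, and is not stated as an exposure formula.
- Some overlap for Japan may be intended. Section 6.1 lists the long-term extension as incorporating the Japan extension, and Section 1 plans 3.5 years for Japan on that basis. Section 7.4.1.3 also refers to a 28-week analysis that is not among the four planned, so it does not show who is expected at the Week 24 lock.
- A reader might infer that Week 24 event rates will look too low. The readable plan does not support this: Week 24 adverse events are reported as numbers and percentages (7.6.1), with risk differences for events of interest (7.6.2).

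**Conclusion.** The section is defective on each reading of its wording. Literally, it inflates open-label exposure for subjects in an extension at the cutoff: 562 days against 196 at an assumed 365 days, and 225 against 196 at an assumed 28 days. Read narrowly, it gives those subjects no value. Completers who entered no extension have no formula in 7.4.1.2 either way.

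The consequence is modest. Only descriptive exposure summaries in the Week 24 report are touched. Efficacy is unaffected, and so are the per-100-person-year rates in 11.7, which belong to Appendix 3 with its own capped open-label formula. It is tempting to report total exposure as 65% too high (928 ÷ 562 = 1.65), but that sum is not a planned output: 11.5.1.4 computes cumulative abatacept exposure only at the final analysis. Section 7.8 does place adverse events for the cumulative abatacept period in the Week 24 report, so someone might set the period exposures beside them, but the plan specifies no such calculation.

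The per-subject figures rest on assumed cutoffs and on-schedule visits. The number of subjects in an extension at the lock is not given, so no table-level effect can be stated.

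**What to change.** Use the SAP's own Appendix 3 rules in the Week 24 text.

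1. In 7.4.1.2, if the next period was entered within 56 days of the last open-label dose, exposure = first dose of the next period − first open-label dose. If it was not, exposure = (last dose − first dose + 1) + 56, whether the subject completed or discontinued.
2. Limit the cutoff formula to subjects still in that same period at the cutoff.
3. In 7.4.1.3, apply the 11.5.1.2 rules in the same way and correct the reference to a 28-week analysis.
4. State whether Japan open-label extension time is meant to be included in the long-term extension figure, and make 6.1, 7.4.1.3 and 7.4.1.4 agree.

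The cost is SAP wording and a change to the exposure derivation. No new data are needed, because 6.1 already says how doses are assigned to periods.

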7.4.1.3 Exposure during Open-Label Extension Period

The exposure to study drug during the open-label extension period will be calculated as follows:

Exposure to study drug in days for subjects who discontinued open-label extension period prior to the analysis cutoff date for the 28-week analysis is calculated as:

- Exposure in days = (date of last dose of study drug in the open-label extension period - date of first dose of study drug in open-label extension period + 1) + 56.

For subjects who are continuing beyond the analysis cutoff date for the 28-week analysis exposure is calculated as:

- Exposure in days = (data cutoff date - date of first dose of open-label extension period + 1).

The start date of the OLE period is not recorded for Japan subjects but is assumed to be the end date of the OL period.

7.4.1.4 Exposure during Long-Term Extension Period

The exposure to study drug during the long-term extension period will be calculated as follows:

Exposure to study drug in days for subjects who discontinued long-term extension period prior to the analysis cutoff date for the 24-week analysis is calculated as:

- Exposure in days = (date of last dose of study drug in the long-term extension period - date of first dose of study drug in long-term extension period + 1) + 56.

For subjects who are continuing beyond the analysis cutoff date for the 24-week analysis exposure is calculated as:

- Exposure in days = (data cutoff date - date of first dose of long-term extension period + 1).

7.4.2 Discontinuation of Study Therapy

Discontinuation from study medication is defined as subject's termination of the study medication (abatacept or placebo) without resumption prior to study completion. A subject will be considered as discontinued from study period if and only if the subject status CRF page indicates he/she did not complete either of the study periods. A separate subject status CRF page is completed at discontinuation or end of (1) double-blind period, (2) open-label period, (3) open-label extension period and (4) long-term extension period.

The number of subjects who discontinue during each of the 4 analysis periods; together with the reasons for discontinuation will be summarized by the randomized group as described in [Section 7.3.1](#). The reasons for discontinuation will be taken from the subject status pages of the CRF for each period.

[REDACTED]

